7.4.2 Risk Assessment

The research involves the collection of information from parents, children and teachers. The risk of participation is considered minimal. There is a potential risk of breach of confidentiality of information and study result about individuals. This risk is made minimal by measures taken by the study team to ensure confidentiality; risks are greatly reduced by using secure files, storing data on secure computers, using unique study identifiers, and deidentification of data prior to analysis. A second risk is that participants become uncomfortable in completing study measures. If this occurs, the protocol will allow participants to stop at any time. Should any specific concerns arise throughout the project period, the CHOP IRB will be promptly informed. Since the purpose of the intervention is to help families clarify their treatment preferences and goals and promote communication between families and clinicians, we expect that serious adverse consequences will be extremely rare and unlikely.

A further risk is that parents may use the portal (intended for non-urgent communication) for urgent behavioral health issues. This risk will be mitigated through direct instruction to parents at the time of consent and portal enrollment, warnings within the portal that it should not be used if immediate attention is needed, and clear guidance in any message transmitted through the portal that it is only meant for routine communication. This approach has proven effective in our prior trial of the MyAsthma portal.

This project will also involve the mapping of geocoded data, which presents a risk of loss of confidentiality if maps are presented. To address this potential problem, and in instances where the number of subjects is less than 5, the CML will work closely with the PI to determine whether geographical masks should be used to protect student confidentiality from identification through deductive or other disclosure that could result from displaying small numbers of students and their school or home locations on a map. Among the techniques that may be applied if the case warrants are microaggregation—replacing the coordinates for a data point by an average of some number of data points similar to them—or blurring—placing data points on an irregular lattice by an ordered list of x and y coordinates and replacing each successive group of 10 with its average. These approaches will be implemented when needed in order to protect the privacy of research subjects.

7.4.3 Potential Benefits of Trial Participation

Patients and parents may benefit directly from inclusion in this study if their preferences and goals are adequately communicated and treatment reflecting those preferences and goals is implemented and adhered to. However, this cannot be guaranteed. The results of this study may assist health care providers in caring for patients in terms of fostering joint decision-making. This model may be replicated in different care settings and other diseases and thus generate generalizable knowledge. Further, the information obtained will be disseminated as widely as possible, including through submission for publication in peer-reviewed journals and presented at scientific and lay conferences.

The investigative team's prior research found that families who were more easily able to contact their child's doctor outside of office visits were more likely to report high levels of SDM, suggesting that interventions that facilitate communication and information sharing outside the context of office visits may improve SDM and engagement in care ([name] et al., 2010). However, the bulk of research and conceptual work on SDM has focused on a single point-in-time decision in a single patient-provider interaction (Brinkman et al., 2011; O'Connor et al, 2009). This study broadens the definition of SDM by focusing on a chronic childhood condition (ADHD) with longitudinal decision-making between patients/parents and multiple providers. By recognizing patients and parents as experts, prioritizing their treatment preferences and goals, and necessitating information sharing over time across the health and school systems that impact all children, SDM in ADHD is an ideal prototype to define strategies to foster patient-centered care, engagement, adherence, and improved outcomes in varied pediatric chronic conditions (e.g. asthma, depression). As such, the lessons learned regarding interventions to foster SDM in ADHD in this protocol are likely to yield generalizable knowledge for fostering patient-centered pediatric care.

7.4.4 Risk-Benefit Assessment

Patients and parents may benefit directly from inclusion in this study if their preferences and goals are adequately communicated and treatment reflecting those preferences and goals is implemented and adhered to. However, this cannot be guaranteed. The results of this study may assist health care providers in caring for patients in terms of fostering joint decision-making. This model may be replicated in different care settings and other diseases and thus generate generalizable knowledge. Further, the information obtained will be disseminated as widely as possible, including through submission for publication in peer-reviewed journals and presented at scientific and lay conferences. Given the minimal risk nature of the study and the potential for benefit, the risk:benefit ratio is considered favorable.

7.5 Recruitment Strategy

To obtain an unbiased sample, a stratified random sample of 300 eligible parent-child dyads will be drawn from participating practices taking into consideration the race/ethnicity/gender of the patients they serve to achieve a representative sample of children from the greater Philadelphia area. Physicians will distribute recruitment flyers to eligible families who are interested in learning more about the study to direct them to contact the research team for more information. Families will also be mailed recruitment letters signed by their primary care provider (PCP) or practice. Included in the mailing will be a stamped self-addressed postcard to permit families to opt out. Families who do not opt out will be called to screen

for eligibility and schedule a consent visit. We will randomly select additional children from the same strata for any families that opt out and if recruitment targets are not met. Families who consent to participate will be contacted at baseline, 3-5 months, 6-8 months, and 9-12 months to complete study measures using all available means including letters, telephone calls, text messages, and emails to ensure data are collected thoroughly and systematically from all participants. Contact information on each participant will be updated every 3 months using interpersonal exchanges and clinic EHR records. Participation incentives will include compensation to complete study measures, quarterly newsletters, and child birthday card mailings, all of which have been used in our prior work with urban populations to maintain >80% participant follow-up ([name] et al., 2010).

Informed Consent/Assent and HIPAA Authorization

7.5.1 Consent

Eligible children and their parents will be identified using electronic health record data and sent recruitment letters from their participating practices. Those families that do not return opt out postcards will be called by the study team to explain the study, screen for eligibility, and arrange for a consent visit. At the consent visit, parents will be asked to provide informed consent to participate in the study and to sign a HIPAA and FERPA waiver to enable the research team to reach out to individuals involved in their child's ADHD care (Appendix 4). Up to 40 participants previously enrolled in the study will be asked to complete a verbal consent in order to fill out second PFCC measure. Up to 40 participants previously enrolled will be asked to complete a verbal consent before proceeding with the qualitative interview (Appendix 20 Qualitative Interview)

Waiver of Assent

Target population is age 5 through 12. Assent is requested to be waived for participants under the age of 7. Assent will be obtained from children aged 7-12 because they will be completing child PRO measures (Appendix 4).

7.5.2 HIPAA Authorization

At the consent visit, parents will be asked to provide informed consent to participate in the study and to sign a HIPAA and FERPA waiver to enable the research team to reach out to individuals involved in their child's ADHD care (Appendix 4).

7.6 Payment to Subjects/Families

Participation incentives will include compensation to complete study measures, quarterly newsletters, and child birthday card mailings, all of which have been used in our prior work with urban populations to maintain >80% participant follow-up ([name] et al., 2010).

Participation incentives will include compensation of \$100 on a ClinCard to complete parent reported study measures, \$20 in gift cards to complete child reported study

measures, quarterly newsletters, and child birthday card mailings. Parents will receive the compensation listed above (\$40 for first visit and travel, \$10 for second visit, \$20 for third visit, and \$30 for fourth visit) for the completion of study visits per participant dyads. If subjects do not complete a study survey to completion they will not be compensated for their time. Therefore, only participants who complete all study visits will receive the full \$100. After completing study measures compensation to parents will be processed immediately. Children who complete the Child PROs survey will receive a \$5 gift card upon completing each study visit, earning up to \$20 in gift cards throughout the study.

Participants who complete additional PFCC questionnaire will be paid \$10.

Participants from the intervention arm who complete the satisfaction survey will be paid \$5.

Participants from the intervention arm who complete the qualitative interview will be paid \$40.

All payments will be completed through a refillable ClinCard.

7.6.1 Payments to parent for time and inconvenience (i.e. compensation)

Parents will receive the compensation listed above (\$40 for first visit and travel, \$10 for second visit, \$20 for third visit, and \$30 for fourth visit) for the completion of study visits per participant dyads. Parents who complete second PFCC questionnaire will be paid \$10. Parents who complete the intervention group satisfaction survey will be paid \$5. Parents from the intervention group who complete the qualitative interview will be paid \$40.

7.6.2 Payments to child for time, effort and inconvenience (i.e. compensation)

Children ages 8-12 will receive compensation for completing the Child PROs survey. Children of participant dyads will be compensated up to \$20, \$5 per survey.

7.6.3 Gifts

Families will be sent birthday cards on the child's birthday.

8 PUBLICATION

Caregiver and stakeholder partners will be involved in all dissemination activities. They will co-author manuscripts and participate in presentations at scientific and lay conferences. These conferences may include the Pediatric Academic Societies annual meetings where new pediatric science is presented and local meetings of the Parents Informed Network and the Philadelphia Department of Behavioral Health. Caregiver and stakeholder partners will participate with the research team in planning dissemination strategies. These will include a mixture of papers, reports, and presentations both locally and nationally. Caregiver and

stakeholder partners will be involved in disseminating their study results through their local employers (e.g. CHOP practices, local school districts) and through their affiliated societies.

The following groups have been identified as key stakeholders for this project: 1) Pediatric patients with ADHD and their caregivers; 2) Clinical providers, including primary care physicians, social workers, case managers, psychiatrists, and therapists who manage ADHD; and 3) Educators, including teachers, guidance counselors. Our dissemination strategy prioritizes dissemination to these groups of stakeholders and to the broader public and scientific community in order to facilitate implementation of the findings among these groups in real-world settings (PC-4). This strategy will be facilitated by the inclusion of caregiver and stakeholder partners representing these groups on our research team and separate stakeholder groups (caregivers, teachers, clinicians) composed of 5 individuals each who will meet on a quarterly basis during the contract award period. Our stakeholder partners include [name], MSS, LSW and [name], BS (caregiver partners), [name], EdD (teacher stakeholder), and [name] and [name] (clinician stakeholders).

The research team plans to work closely with key stakeholders to disseminate and implement the findings of the research study into accessible and usable formats in research, clinical and community-based settings, including schools and pediatric practices. Aspects of the proposed research plan that facilitate dissemination include the implementation of an electronic ADHD portal that can be adapted for other EHRs, a Care Manager intervention that is manualized and thus transportable to other health care settings, and the use of patient-centered outcome measures written in an easy-to-read, user-friendly, low-literacy format that can be adopted by health care institutions to assess ADHD treatment.

The study team plans to work with the following local and national partners to disseminate findings from this study. These partners were identified by members of our research team including our caregiver and stakeholder partners.

- PolicyLab: Center to Bridge Research, Practice and Policy: Drs. [name] and [name] are both PolicyLab faculty. PolicyLab has a strong track record of engaging policymakers on issues related to child health and utilizes evidence-to-action briefs, social media, and in-person meetings and congressional testimony to translate findings to policymakers. The center has a staff composed of attorneys, strategy specialists, public relations staff, and public health and policy staff that provide expertise in dissemination. We will work with PolicyLab staff to strategize dissemination to policymakers and child health advocates.
- Department of Behavioral Health (DBH)/Office of Medical Assistance Programs (OMAP): DBH manages the Medicaid managed behavioral care program in Philadelphia, covering 75% of children in Philadelphia. [name] is actively engaged with this department and will present study findings to coordinate dissemination locally throughout the city. OMAP administers the Medicaid program in the commonwealth of Pennsylvania. [name] will reach out to state administrators at OMAP to disseminate study results.
- American Academy of Child and Adolescent Psychiatry and the American

 Psychological Association: Drs. [name] and [name] are members of these organizations and will plan to present results at national meetings of these groups to

- engage these specialists in conversations regarding study findings and efforts to broadly implement approaches proven effect in the proposed trial.
- Pennsylvania (PA) Medical Home Program, also known as "Educating Practices in Community Integrated Care (EPIC-IC)", is a collaboration between the PA Department of Health and the PA Chapter of the AAP designed to enhance the quality of life for children and youth with special health care needs through effective community-based care coordination and improved primary health care. [name] will work with the PA Medical Home Program to disseminate findings to primary care practices in the state.
- American Academy of Pediatrics: The AAP is the largest pediatric professional organization in the U.S. Drs. [name], [name], and [name] are AAP Fellows and will work with the AAP to disseminate study findings to a national audience of practicing pediatricians including presenting findings at the AAP National Convention and Exhibition and disseminating results through its newsletter and section programs. In addition, [name] is a member of the AAP's Child Health Informatics Center is a primary vehicle for communication between practicing pediatricians and the EHR vendor community and will work through CHIC to disseminate study findings and provide EHR vendors with specifications to implement the portal.
- Children and Adults with Attention-Deficit/Hyperactivity Disorder (CHADD) is the largest family-driven education and advocacy group for affected families. Drs. [name] and [name] have previously collaborated with CHADD and plan to reach out to CHADD leadership to disseminate findings to a national audience of families with ADHD.
- Parents Informed Network (PIN): [name] is Director of PIN in Southeastern Pennsylvania. She will assist in disseminating study results to parents and families in this area that are members of PIN through newsletters and their website.
- CHOP Parent Advisory Group: [name] is a member of the Parent Advisory Group and will work to disseminate study findings to other parents in the CHOP clinical practice network.
- Local school districts and the Pennsylvania State Education Association (PSEA): [name] is a teacher in the Chichester School District in suburban Philadelphia and a member of PSEA. She will work to disseminate findings locally and state-wide to teachers, to create professional development activities for teachers (Act 48 credit) based on project findings, present at Home and School Association Meetings, and would draft a publication for the Council for Exceptional Children publication.


We conducted sensitivity analyses to examine the impact of preference and treatment intensity on the main outcome of ADHD symptoms. We stratified tier 2 participants by intervention dosage (frequency of interaction with the portal/care manager): 0-1 sessions, 2 sessions, or 3 or more sessions. We compared differences in ADHD symptom score changes over time by intervention dosage using a linear mixed effects model that adjusted for seasonality.

Aim #2: We originally proposed to assess whether family engagement, treatment initiation and adherence were mediators of intervention treatment effects: This analysis proposed to focus on the role of engagement and treatment initiation at 3 months or adherence at 6 and 9 months as mediators of the effect of the intervention on the study outcomes. Since none of the primary or secondary outcome measures were different between groups, we elected not to proceed with formal tests of mediation. Instead, we assessed for differences in family engagement and treatment initiation and adherence between groups. For each of the above sets of potential mediators, we report distributions by case/control as assess bivariate differences via t-tests or contingency tables/Chi-square analyses where appropriate.

In order to assess family engagement, a series of items were created from review of the literature and prior instruments in other fields. We utilized confirmatory factor analyses to find distinct domains for which each item loading was greater than 0.7. Our first round of analyses resulted in 3 factors: patient/family centered care, communication, and understanding. Upon presentation to the study team, there were several items that were dropped from the initial domains, but additional items resonated with the team as important concepts in which the intervention was focused. Thus, the study team came to consensus on items that should be included. These items represented four conceptual domains. The 4factor structure was supported in confirmatory factor analyses. While the patient/family centered care and understanding domains remained the same, the original communication domain was split into two factors, resulting in the following domains: care team accessibility; patient and family-centered care; communication among members of the care team, and understanding of ADHD. To compare patients in the tier 1 and tier 2 groups by engagement status, we utilized t-tests for each of the four domains separately. Further, linear mixed effects models were implemented for each engagement domain as the outcome, with intervention status and season as covariates clustering for clinic site. We further assessed for item responsiveness using item response methods.

We explored treatment initiation and adherence via the services assessment for children and adolescents (SACA) and medication status.⁹⁵ On the SACA, patients reported service use ever, as well as service use within the past 9 months. Categorizations include any service use, ambulatory service use (any community mental health or outpatient clinic, private professional, or in-home provider), and overnight stay (psychiatric or medical unit, residential treatment center, group home, or foster home). Differences between intervention groups and treatment initiation were assessed via Chi-square tests. In addition, treatment initiation and adherence were assessed via medication status throughout the study period. At baseline and 3, 6, and 9 month follow up surveys, participants were asked as to whether their child was on or off medication. If data was missing for a particular timepoint, we utilized medication status within the EHR if available.

Aim #3: To explore individual, family, and community factors that moderate treatment effects, the same longitudinal data models supported estimates of effect modification by means of 3-way interaction terms of time-by-treatment-by effect modifier as well as subgroup analyses. Factors of importance explored in this aim included parent education level (high school vs. less than high school), race/ethnicity, medication status, and neighborhood variables (median income, metropolitan status). To obtain the community level variables, each participant was geocoded via street address, city and ZIP code. American Community Survey Census tract level information including median income, percent high school graduation, population density, and percent poverty were linked to participant tracts. Urbanicity was defined as home residence in Philadelphia County (urban) vs suburban county. Bivariate differences between intervention status and the above factors were assessed utilizing Chi-square tests for categorical characteristics, and t-tests/Wilcoxon rank sum tests for continuous characteristics.

Moderation models and stratified models were conducted separately for each

outcome, following the same modeling strategy in Aim 1 with GEE (marginal) models accounting for clinic site and seasonality.

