1.2 Name and Description of Investigational Product or Intervention

This intervention includes the EHR-linked portal created for ADHD patients, in addition to care mangers as a means to improve SDM and care of ADHD patients. Using data captured through the portal, the CM will meet with families at the beginning of the study to confirm their treatment preferences and goals, provide additional education on ADHD treatment, and distribute handouts on common concerns among ADHD patients and families. The CM will contact families weekly to every 3 months by phone, email, or in-person as needed to assess treatment use, identify new concerns, and assist families with problem-solving. Using the portal or other means, the CM will also communicate with pediatric clinicians, mental health providers, and teachers to clarify family treatment preferences and goals and address emerging treatment issues. A fidelity checklist developed in the pilot study will be utilized to assess self-reported task completion of each intervention component by the CM (0- not completed, 1- partially completed, 2- fully completed). In addition, the CM will summarize clinically relevant encounters in the ADHD portal, facilitating communication.

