(Tier 2) Patient portal with CM to facilitate SDM and promote adherence (Appendix 2): The use of a patient portal combined with a CM addresses the potential limitations of reliance on technology alone to communicate information (Michel et al., 2015; Jackson, Cheater, & Reid, 2008). The CM provides an individual responsible for communicating information and facilitating coordination of care. Using data captured in the portal, the CM will meet with families at the beginning of the study to confirm their treatment preferences and goals, provide additional education on ADHD treatment, and distribute handouts on common concerns among ADHD patients and families. The CM will contact families weekly to every 3 months by phone or in-person as needed to assess treatment use, identify new concerns, and assist families with problem-solving. Using the portal or other means, the CM will also communicate with pediatric clinicians, mental health providers, and teachers to clarify family treatment preferences and goals and address emerging treatment issues. A fidelity checklist developed in the pilot study will be utilized to assess self-reported task completion of treatment components by the CM (0- not completed, 1- partially completed, 2- fully completed). In addition, the CM will summarize clinically relevant encounters in the ADHD portal, facilitating communication.

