5.3.2 Efficacy Analysis

Primary analyses will be based on an intention to treat approach and will include all subjects as randomized. We will follow usual guidelines for reporting results (CONSORT)

(CONSORT Group, 2010), and will report all outcomes in both absolute (how much change) and relative terms (percentage change). In sensitivity analyses to examine the impact of preference and treatment intensity, we will look at the effects of the intervention stratified by baseline preferences and intervention dosage (frequency of interaction with the portal/CM).

The primary endpoints will be the change in ADHD Symptoms (as measured by the VPRS and VTRS) and the change in Goal Attainment (as determined by the treatment goals of the patients and their families) between baseline and the 3-5, 6-8, and 9-12-month points.

• Secondary endpoints will include the change in PROs, which parents of children with ADHD and teachers have identified as most important: school performance, student engagement, peer relationships, family belonging, and teacher connectedness. In addition, PFCC measure will be examined for internal consistency with test-retest reliability. The satisfaction survey will measure how satisfied parents in the intervention arm were with the services provided by their care manager. The qualitative interview will evaluate outcome experience and feedback in the intervention group with care management.

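### The Tier 2 dosage sensitivity analysis compares non-randomised session groups with season as the only named covariate, so severity, need and engagement can appear as a dose effect in either direction.

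*SAP*

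**What the plan says.** The SAP (Aim #1, sensitivity-analysis paragraph) gives the purpose as "to examine the impact of preference and treatment intensity on the main outcome of ADHD symptoms". The exposure is sessions received, in Tier 2 only: "We stratified tier 2 participants by intervention dosage (frequency of interaction with the portal/care manager", with the groups given as "0-1 sessions, 2 sessions, or 3 or more sessions". The model is stated in one sentence: "We compared differences in ADHD symptom score changes over time by intervention dosage using a linear mixed effects model that adjusted for seasonality".

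The preceding Aim #1 paragraph lists a longer covariate set for the main models: age, gender, race/ethnicity, school lunch, metropolitan status, SSI, parent education, school type and medication status. The dosage paragraph does not repeat it. The same Aim #1 paragraph puts clinic site in every model as a random effect, so site is probably in the dosage model too. It also treats the baseline score as one of the repeated outcomes.

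Protocol 5.3.2 announced the analysis in general terms: "we will look at the effects of the intervention stratified by baseline preferences and intervention dosage". It gives no confounder set. On what determines contact, Protocol 1.2 says "The CM will contact families weekly to every 3 months by phone, email, or in-person as needed to assess treatment use, identify new concerns", and Protocol 4.2 is similar: "The CM will contact families weekly to every 3 months by phone or in-person as needed to assess treatment use".

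**The concern.** Randomisation protects the comparison of Tier 2 with Tier 1. It does not protect a comparison of Tier 2 families with one another by how many sessions they had. With Tier 1 left out, no randomised contrast remains. Session count arises after randomisation and can reflect how severe the child was at entry, what problems arose later, and how engaged the family was. Each of these may also relate to symptom change.

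The wording of the purpose is causal, and neither document cautions that the result is only an association. The SAP (Aim #2) reports that no primary or secondary outcome differed between the arms. In that setting, a gradient favouring more sessions could be taken to show that the care manager works for families who use the service. A gradient the other way could be taken as harm, or could hide a real benefit.

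**Working it through.** The documents give no estimate, sample size or power for the dosage analysis, so there is no figure of its own to reproduce. The size of the possible bias can be illustrated from the planning values.

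**Inputs from Protocol 5.5**
- SD of the Vanderbilt score: 6, with 5 as the alternative.
- Correlation with baseline: r = 0.8 at 6-8 months and r = 0.6 at 9-12 months.
- Difference for which power of 0.87 is quoted: 2.5 points at SD 6.
- Evaluable children per arm: 120.

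**Assumptions not in the documents**
- The three session groups are thirds (about 40 children each).
- There is no true dose effect.
- Session count correlates with baseline severity at rho = 0.2, 0.3 or 0.5, and is related to later scores only through baseline.

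**Regression to the mean.** The mean of the top third of a standard normal variable is 1.091. The gap in mean baseline between the highest and lowest session groups is therefore 2 × 1.091 × rho × SD. With equal SDs at both visits, a fraction (1 − r) of that gap is lost by follow-up:

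spurious difference in improvement = 2 × 1.091 × rho × SD × (1 − r)

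| rho | Baseline gap, SD 6 | 9-12 months (× 0.4) | 6-8 months (× 0.2) |
|---|---|---|---|
| 0.2 | 2.62 | 1.05 | 0.52 |
| 0.3 | 3.93 | 1.57 | 0.79 |
| 0.5 | 6.55 | 2.62 | 1.31 |

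A simulation of the change score to 9-12 months (4,000 replicates, 120 children, remaining correlations assumed) gives 1.04, 1.55 and 2.60 points. The corresponding false-positive rates are 13%, 25% and 59%, at an assumed two-sided 5% level.

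**Contact that follows the course of symptoms.** Here a positive difference means the group with most sessions did worse.
- If worsening up to 6-8 months prompts contact (weights 0.3 and 0.5), the spurious difference is +2.47 and +4.12 points. With baseline in a change-score model, +1.99 and +3.35 remain.
- If children who improve have more contact (weight −0.3), it is −2.47, and −1.98 after baseline adjustment.

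The sign therefore depends on what drives contact, and baseline adjustment removes only the part due to baseline severity.

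**Does adding baseline VPRS as a covariate help?** Not if baseline is also an outcome. The dose-by-time term then compares within-child changes. A covariate that is constant within a child shifts all of that child's visits equally and cancels, exactly so in complete balanced data. Simulations at rho = 0.3 gave a spurious last-visit difference of about −1.5 to −1.6 points, the same with and without baseline as a main effect. It fell to between 0.01 and −0.1 only when the follow-up scores alone were the outcomes and baseline was interacted with visit.

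**The case against.** The strongest reply has four parts.

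*It is a labelled sensitivity analysis, announced in the protocol, and the SAP draws no causal conclusion from it.* This stands. It limits the consequence, but the stated aim is still the impact of intensity, with no caution on interpretation.

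*The documents do not prove that sessions follow severity.* In Protocol 4.2 the phrase about need may qualify the mode of contact, and other places give the frequency without it. The slowest schedule, one contact every 3 months, gives 9 / 3 = 3 contacts over 9 months besides the initial meeting. If sessions are these contacts, the two lower groups mainly reflect low uptake. This stands as far as the mechanism goes: severity-driven contact is a plausible assumption, not a documented fact. Low uptake is itself self-selection, so the groups remain non-comparable.

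*The model compares changes and includes clinic site.* Comparing changes removes a constant difference in level. It does not remove regression to the mean or need that arises later. Site does not measure a child's severity or a family's engagement.

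*The full Aim 1 covariate list may have been intended.* If so, the SAP should say so. That list has no separate term for emerging need or engagement.

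Two stronger readings are tempting. A reader might infer that families who left early could not reach the highest group. The documents do not support this: contact could be weekly, so three sessions could occur in the first month. Early leavers are at most less likely to reach it. A reader might also infer that the analysis will favour the care manager. The direction cannot be told from the documents, and no dosage result appears in them.

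**Conclusion.** The concern holds as one of confounding and interpretation. As written, the dosage contrast is non-randomised, and season is its only named covariate. Under the stated assumptions, regression to the mean alone gives about 1.0 to 2.6 points at 9-12 months and about 0.5 to 1.3 at 6-8 months, against the 2.5-point planning difference. Contact that follows the child's course could add to this or reverse it. All these figures rest on an assumed strength of association and on equal thirds, so they show what is possible and do not estimate the bias in this trial.

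The documents do not support extending the point to the main result: the intention-to-treat comparison does not use session counts and is unaffected.

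**What to change.** 1. Model the 3-, 6- and 9-month scores as outcomes, with baseline VPRS interacted with visit. Do not enter baseline as a main effect while it is also an outcome.
2. Add the Aim 1 covariates and state the full covariate list, including clinic site.
3. Count only the sessions that precede each outcome.
4. Report the three-group comparison as a descriptive, non-randomised association, and say that need arising during follow-up remains uncontrolled.

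The cost is a small re-analysis of data already collected and a weaker claim.

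An instrumental-variable analysis with assigned arm as the instrument is optional. It would keep randomisation but give a wider interval. For a threshold of three sessions its exclusion assumption is doubtful, because assignment could also act through the initial meeting, through one or two sessions, or through the care manager's contact with clinicians and teachers.
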